Animal models provide direct evidence of this pathophysiological effect. In healthy animals, splanchnic nerve stimulation shifts blood into the central compartment, increasing preload and cardiac output. In dogs with cardiac pacing induced systolic heart failure, splanchnic vascular capacitance was decreased (Ogilvie RI, circulation 1992). In these dogs, surgical transection of the splanchnic nerve, terminating sympathetic tone, results in decreased preload as

measured by systolic and diastolic filling pressures and increased compliance of the left ventricle (Figure A). In humans splanchnic nerve blocks are commonly used for pain control in patients with intractable visceral organ cancer pain. The nerve blocks are done temporarily using anesthetic agents or more commonly permanently using neurolytic agents. Interestingly, the most common "sideeffect" of this therapy includes transient orthostatic hypotension due an increase in splanchnic vascular storage capacity, which typically is prevented by aggressive pre-procedural hydration (Eisenberg E, Anesthesia and analgesia 1995).

А

В

[figure not shown]

Figure B: Pressure-volume recording in left ventricle in same animal. Blue curves are the baseline recordings and red indicate pressure-volume loops after nerve transection. Nerve transection caused flattening of the end-diastolic pressure-volume relationship indicating higher compliance. Unpublished pilot data.

In addition to the strong evidence supporting splanchnic nerve blockade as treatment of volume overload, it is possible it will also treat cardiorenal syndrome. The autonomic nervous system plays a critical role in the regulation of the kidney. Though this system is not fully understood, preclinical and clinical studies indicate the presence of a hepatorenal reflex that inhibits the renal function and causes fluid retention. This reflex has its origin in the portal vein and is stimulated by portal congestion. The splanchnic nerves represent the afferent and partially the efferent arm of the reflex arch. Inhibition of this reflex pathway in animals and a small human pilot study was shown to improve renal function and urine production.

4. Design & Procedures:

This study will be a prospective, uncontrolled clinical trial. The study will not be controlled as invasive monitoring of hemodynamics will be performed, allowing clear demonstration of a cause-effect relationship. Furthermore, the goal of the study is to demonstrate proof of concept.

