This study aims to piggy-back on an elective right heart catheterization (+/- left heart catheterization) in patients admitted for acute decompensated heart failure The right (+/- left heart catheterization) will be part of the subject's standard of clinical care (SOC). Subjects will undergo catheterization of the heart to obtain central cardiac pressure and other cardiac hemodynamic parameters found to be necessary by the primary team. This will occur in the cardiac catheterization lab. Once the SOC catheterization procedure is completed the subject will undergo, as part of this clinical study (CS), a regional nerve block (bilateral splanchnic nerves) while they are in the catheterization lab. This will be performed by an anesthesiologist experienced in splanchnic nerve blocks. Routinely, patient will remain in the catheterization lab for the duration of anesthetic block and will be continuously hemodynamically monitored. Also, prior to elective catheterization procedure and following splanchnic block patients will undergo a number of vital, laboratory and imaging tests, which will be in parts SOC or part of the CS (see Table of Assessments below).

Table of Assessments

Table of Asses	Silicitits						
Required Assessment	<5 Days before procedure	Same day of procedure (<12h before procedure)	Procedure (1-1.5h)	Within 2 hours after Procedure	Day after procedure	48 h after procedure	6 Months after Procedure (±14 days)
Vitals (BP, HR, RR, SpO2)	X (SOC)	X (SOC)	X (SOC)	X (SOC)	X (SOC)	X (SOC)	
Weight	X (SOC)	X (SOC)		X (SOC)	X (SOC)	X (SOC)	
Orthostatic vitals	X (CS)			X (CS)	X (CS)		
Urine output (continuous recording)	X (SOC)	X (SOC+CS)	X (SOC)	X (CS) 3 and 8 hours post procedure	X (SOC+CS)	X (SOC+CS)	
Labs: BMP, pro-BNP, urine sodium,		X (SOC/CS)		X (CS) for pro-BNP and urine sodium	X (SOC) for BMP	X (BMP are SOC, no pro BNP needed)	
Labs (Angiotensin II), Plasma Metanephrines, Vasopressin, Plasma Catecholamines		X (CS)		X (CS)			
Dyspnea Questionnaire		X (CS)	X (CS)	X (CS)	X (CS)	X (CS)	
Six minute walk test	X (CS)	(03)	(03)	(CS)	X (CS)	(CS)	
Impedance and lung fluid content measurement			X (CS)	X (CS)			
Positional Change: Bending Over		X (CS)		X (CS)			
Positional Change: Leg Raise			X (CS)				
Heart rate variability	X (CS)	X (CS)	X (CS)	X (CS)	X (CS)	X (CS)	
Echocardiogram	X (SOC)			X (CS)			
Splanchnic nerve block			X (CS)				
Phone Call**	1 · · · · · · · · · · · · · · · · · · ·						X (CS)

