*Plasma Metanephrines will be performed only if subject is on inotropes **Phone call will capture mortality status and number of subject admissions to the hospital since procedure

Following enrollment into the study the subject will undergo the following tests/measurements. A majority of the clinical testing occurs as part of routine clinical care and will be marked as SOC (like in the above table). Tests required only for the purpose of the study are marked with CS.

Pre-procedure: Following information will be collected from the patient charts that will

- be done as standard of care (SOC). Study specific tests/recordings are also listed below:
- If the subject is female and childbearing potential and has not had a pregnancy test since the arrival to the hospital, a blood pregnancy test will be done (CS). If positive the subject will be excluded from the study.
- Subjects will have strict measurement of urine output (SOC). Additionally, subjects will be asked to void 3 hours prior to their procedure. They will be asked to void again immediately prior to the start of the procedure. A urine sample will be sent to the laboratory to check for the sodium concentration (CS). Subjects requiring a foley catheter will have measurements taken at comparable time intervals (SOC).
- Recorded vitals including weight, BP, HR, RR, SPO2 on the day before procedure and within 1h before procedure (SOC) and record heart rate variability using a non-invasive wrist monitor for 5 minutes (CS).
- Orthostatic vitals (5 minutes supine, 1+5 minutes sitting and 1+5 minutes standing) on the day before procedure and within 1h before procedure (CS)
- Labs: Basic metabolic panel (BMP) (SOC), brain natriuretic peptide (BNP) (SOC/CS), plasma angiotensin II (CS), plasma arginine vasopressin (CS), plasma catecholamines. Plasma metanephrines (CS) will be performed if subject is on inotropes. This will not require an extra lab draw. Total expected blood loss is <20ml.
- Dyspnea questionnaire using a 7-point Likert scale and Visual Analog Scale (CS)
- Six minute walk test (CS)
- Echocardiogram during the admission and no longer than 5 days prior to study (SOC). If no up-to-date echocardiogram is present, a study related Echocardiogram will be obtained (CS).
- If the patient is on diuretics medications the scheduling of the medication will be adjusted to minimize interference with the study intervention.

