2. Bilateral splanchnic nerve block performed by an anesthesiologist (see images below) (CS). Following the right heart catheterization procedure the patient will be prone on the abdomen. Central venous access remains in place. Needle will be placed under fluoroscopic guidance in the posterior chest wall. Anesthetic solution (1% lidocaine with epinephrine) (1:200.000) will be injected (10-15 ml on each side). Patient will then be placed back on his/her back and central

hemodynamics are recorded again for the next 1-1.5 hours, approximately every 15 minutes. The central venous catheter will be removed after the hemodynamic monitoring is completed in the catheterization laboratory. Unless the primary team requested the catheter to remain in place and the patient is moved to the intensive care unit.

Following the block, the subject will repeat the positional change of a leg raise at 30, 60, and 90 minutes post-block to observe any changes in shortness of breath symptoms.

Additional measurements include:

- Orthostatic vitals will be obtained at the end of the hour while in the catheterization lab (CS).
- Dyspnea questionnaire (CS)
- If medically indicated a Swan Ganz catheter will be left in place. This would enable continuous monitoring of central hemodynamics for the next 24h (q4h) (SOC).

Follow up procedures:

Following right heart catheterization and lidocaine splanchnic nerve block the patient will be monitored on the floor/CCU for at least 48 hours following nerve block (SOC).

- Continuous recording of urine output for 24 hours (SOC). They will then be asked to void again 3 and 8 hours after the placement of the nerve block and 24 hours after nerve block (CS).
- Basic vitals (SOC) and orthostatic vitals (CS) within 24 hours after nerve block, and record heart rate variability using a non-invasive wrist monitor (CS).

- Repeat labs 12-24 hours after nerve block (next morning) [BUN (SOC), BMP (SOC) and pro-BNP (CS)
- Labs: Angiotensin 2, plasma metanephrines (if on inotropes), plasma catecholamines, vasopressin and urine sodium will be collected immediately before and after the procedure
- Dyspnea questionnaire at 12-24 hours after nerve block (CS) and again at 48 hours
- Six minute walk test (CS) within 24 hours after block and again at 48 hours
- Weight the next morning after nerve block (SOC) and at 48 hours.
- Echocardiogram within 1-2 hours after nerve block (CS)

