- Positional change of bending over to evaluate 'bendopnea' (shortness of breath symptoms with bending over).

Phone Call

Subjects will be contacted by study team six months (\pm 14 days) following their nerve block procedure. The purpose of this call will be to obtain mortality status and document the number of inpatient admissions since the procedure.

Blood samples processing:

Some blood samples collected before and after the nerve block (plasma metanephrines, plasma catecholamines, angiotensin II and arginine vasopressin) will be processed (centrifuged) and stored at -70 degrees Fahrenheit before sent out to an external lab. Storage duration may vary between weeks to months. Samples will be stored in a research freezer located on the 7th floor of Duke North (cath lab research freezer). As part of the study, we will send blood for study-related laboratory tests to the Mayo clinic and Inter Science Institute. These would include laboratory tests such as metanephrines, vasopressin, catecholamines, and angiotensin.

Safety endpoints:

- The duration of the anesthetic block is estimated for 1.5 hours. The subject will be monitored for up to 1.5 hours in the catheterization laboratory (acute safety). Chronic safety up to 48 hours post procedure. Hereby the patient will be observed clinically on the floor or CCU per standard clinical care routine. Further the subject's medical chart will be observed for 6 months following study enrollment to evaluate for recurrent admissions for heart failure.

Incidence of major side effects like:

- Pneumothorax, possibly requiring a chest tube
- Aortic puncture with retroperitoneal bleed or hematothorax
- Spinal cord trauma with possibly paralysis

Incidence of minor side effects like:

- Orthostatic hypotension
- Pain at puncture site and intercostal neuralgia

- Gastrointestinal dysmotility including diarrhea, constipation and abdominal cramping
- Bleeding at puncture site

Efficacy endpoints:

The following efficacy endpoints will be evaluated:

- Primary: Reduction in central venous pressure and/or pulmonary artery pressure (diastolic) and/or pulmonary capillary wedge pressure at 30-60 minutes after nerve block
- Secondary: Increase in cardiac output, improvement in echocardiographic parameters like ejection fraction (increase), central venous pressure (decrease), pulmonary artery systolic pressure (decrease), right ventricular diameter (decrease), left ventricular diameter (decrease)

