 - Reduction in pro brain natriuretic peptide (pro-BNP)
 - Increase in UOP (output measured in ml/hour) and renal function (BUN and creatinine) in the hours following the procedure. Follow up for 48hours
 - Symptomatic improvement like a decrease in dyspnea (dyspnea questionnaire) and 6-minute walk test

5. Selection of Subjects:

Subjects will be recruited from Duke University Medical Center. All potential study subjects are admitted for ADHF and are treated as inpatient on the regular floor or in the intensive care unit.

The study will enroll subjects who meet the criteria as detailed below. Potentially eligible patients will be consented and entered into a screening process, which will include a chart review and physical examination. The primary enrollment target is up to 20 subjects (10 HF with preserved ejection fraction and 10 HF with reduced ejection fraction).

Inclusion criteria:

- Age 18-90
- Established diagnosis of HFpEF or HFrEF
- Admitted to DUMC for decompensated HF (NYHA stage 3-4, Class C-D), including patients on inotropic medication
- Symptomatic with dyspnea with clinical, radiographic or echocardiographic signs of fluid overload
- Planned for elective diagnostic right (+/- left) heart catheterization
- On a stable HF drug regimen prior to admission
- Anticipated hospital stay of at least 2 nights following catheterization procedure

- Preferably "diuretic resistant". Urine output <50ml/hour in the 24 hours preceding enrollment into the study.

Exclusion criteria:

Contraindicated medications:

- Anticoagulation at the time the procedure or in case of recent warfarin use an INR >1.4. Anticoagulation includes: warfarin, or novel oral anticoagulants like dabigatran, rivaroxaban, apixaban, endoxaban or full dose intravenous heparin products or bivalirudin and fondaparinux). Antiplatelet agents besides aspirin such as ticagrelor, prasugrel, Plavix are also considered to be a contraindication if used at time point of procedure.
- Immunosuppressive medications for solid organ transplant

HF medication regimen:

- Initiation of HF medications (in the 48 hours preceding the study) such as beta blockers, ACEI, ARB, aldosterone receptor blockers, calcium channel blockers of any type, central sympatholytics like clonidine, moxonidine,

- Recent acute MI or hemodynamic instability:

- Acute MI (STEMI or Type I NSTEMI) within 7 days?
- Evidence of progressive cardiogenic shock within 48 hours
- Repeat systolic blood pressure <90mmHg or >180mmHg

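### The baseline six-minute walk may be almost five days old, so the before-after comparison on this secondary endpoint includes avoidable days of inpatient treatment

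*Combined protocol and SAP*

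**What the plan says.** - **Baseline walk.** In section 4, Table of Assessments, the one legible pre-block mark for the walk is under "<5 Days before procedure". The same-day column has no legible mark for it. The pre-procedure list in section 4 names the walk without a time, although the vital-sign items in the same list do carry times.
- **Follow-up walks.** Section 4, Follow up procedures: "Six minute walk test (CS) within 24 hours after block and again at 48 hours". The table places a walk on the day after the procedure.
- **Duration of the block.** Section 4, Safety endpoints: "The duration of the anesthetic block is estimated for 1.5 hours".
- **Role of the walk.** It is among the secondary efficacy endpoints: "Symptomatic improvement like a decrease in dyspnea (dyspnea questionnaire) and 6-minute walk test".
- **Design.** "This study will be a prospective, uncontrolled clinical trial". The reason given is: "The study will not be controlled as invasive monitoring of hemodynamics will be performed, allowing clear demonstration of a cause-effect relationship".
- **Analysis.** Section 12 plans paired t-tests of change from baseline at two-sided 0.05, with no adjustment for time or concurrent treatment.
- **Concurrent treatment.** All subjects are inpatients treated for acute decompensated heart failure (section 5). Diuretics are retimed around the procedure but continue, and other drugs may continue (section 4).

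**The concern.** A paired comparison in a single arm attributes to the intervention everything that changes between the two measurements. Here that includes the block and all the inpatient treatment given between the walks. The longer the interval, the larger the share of change that may come from usual care.

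The protocol's reason for having no control is invasive haemodynamic monitoring. That argument fits the primary endpoint, which has a baseline immediately before the block and a reading at 30-60 minutes. It does not carry over to a walk test whose two measurements may be days apart.

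Some treatment drift is unavoidable, because the follow-up walks come a day or two after the block. The part that accrues before the block is avoidable and comes only from the width of the baseline window. At stake is whether a significant gain in walk distance could be read as symptomatic benefit of the block when it is partly or wholly ordinary recovery.

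**Working it through.** **Plan's own figure.** The documents give no power, SD or expected change for the walk. The only calculated figure is power of 0.90 for a 25% fall in central venous pressure with 16 subjects. It cannot be reproduced because no SD is stated, and this point does not depend on it. Only n = 16 is taken from it.

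**Step 1: longest interval between walks** (from the table and text in section 4)

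- To the 24 h walk: under 5 × 24 + 24 = 144 h, so under 6 days.
- To the 48 h walk: under 5 × 24 + 48 = 168 h, so under 7 days.
- The 1.5 h block is 1.5/144 = 1.0% and 1.5/168 = 0.9% of these intervals.

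With a baseline no more than 24 h before the procedure, the limits are 24 + 24 = 48 h (2 days) and 24 + 48 = 72 h (3 days).

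**Step 2: assumptions** (none of these is in the documents)

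- Usual care adds 5-10 m per day, linearly.
- The SD of the paired change is 50-80 m.
- The block has no effect on walk distance.

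**Step 3: drift = rate × days**

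| Interval | Days | Drift |
|---|---|---|
| Now, to 24 h walk, worst case | 6 | 30-60 m |
| After the fix, to 24 h walk | 2 | 10-20 m |
| After the fix, to 48 h walk | 3 | 15-30 m |

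**Step 4: chance of a false improvement.** The paired t statistic follows a noncentral t with 15 degrees of freedom and noncentrality (drift/SD) × √16. Improvement is declared when t exceeds 2.131. With no drift the chance is 2.5% in that direction.

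| Drift | Noncentrality, SD 80 / SD 50 | Chance, SD 80 / SD 50 |
|---|---|---|
| 10 m | 0.50 / 0.80 | 7% / 11% |
| 15 m | 0.75 / 1.20 | 10% / 20% |
| 20 m | 1.00 / 1.60 | 15% / 32% |
| 30 m | 1.50 / 2.40 | 29% / 61% |
| 60 m | 3.00 / 4.80 | 80% / 99% |

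The 60 m row, and the 30 m row when read as the present schedule, apply only if every subject's baseline is at the outer limit of the window. They bound the problem and are not an expected error rate.

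**Step 5: comparison within the protocol.** The dyspnea questionnaire, the other symptom measure in the same endpoint, has a same-day baseline in the table. The walk does not.

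**The case against.** **The table may not mean what it seems to.** The walk row is damaged in the extracted text, with loose fragments in cells that carry no mark. They match the cells of the dyspnea row above, and one falls under the procedure itself, where a walk is implausible, so they are probably spill-over. For the same reason, the lack of a legible 48 h mark is not treated here as a conflict with the text. Orthostatic vitals also have their only pre-procedure mark in the five-day column, yet the text times them to the day before and the last hour. The column could therefore be a general pre-procedure slot. This stands as a reason to expect tighter practice in some cases. It does not supply a limit for the walk, and for the echocardiogram in the same column the text confirms a true five-day window.

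**Many baselines will be recent.** The walk is a study test done after enrolment. For a next-day catheterization, consent is due before midnight so that pre-procedural tests can be done (section 7). This stands: five days is the outer bound, not the typical case.

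**There is some mitigation.** Heart failure drugs started in the preceding 48 h are an exclusion, and diuretic-resistant patients are preferred (section 5). This is partial. The exclusion does not name diuretics and covers less than five days.

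**The root cause is the missing control, which the protocol accepts for proof of concept.** This stands, and it is why moving the baseline reduces the confounding without removing it.

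**A lasting benefit is expected.** Section 10 anticipates symptomatic benefit that outlasts the block. It gives no data for this, and the present schedule could not separate such benefit from recovery under treatment.

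**A stronger reading about missing walks.** The plan says "If medically indicated a Swan Ganz catheter will be left in place". A reader might infer that these subjects cannot walk, that the sickest drop out of the paired test, and that this inflates the result. The documents do not support that. They nowhere say that a retained catheter prevents walking, catheter access is radial, brachial or cervical, and nothing shows that the lost changes would be smaller than the rest. Giving such subjects a worst rank would also charge a care decision to the block.

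**Conclusion.** The point holds as a scheduling weakness in a secondary endpoint. As written, the plan allows a baseline walk just under five days old, and hence walks just under 6 or 7 days apart, in treated inpatients without a control. The direction of the bias requires only that patients improve on average under usual care.

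Its size cannot be derived from the documents. Under the stated assumptions, the worst-case drift to the 24 h walk is 30-60 m now and 10-20 m with a baseline within 24 h. The residual 10-20 m still gives a false improvement in about 7-32% of trials with 16 subjects, so the fix does not restore the nominal 2.5%. For the 48 h walk the residual is larger, at 15-30 m.

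A reader might go further and infer that an inactive block would usually be declared effective on this endpoint. That would require most subjects to have baselines near the five-day limit and the assumed drift to be true, and the documents show neither. Nor does the point reach the primary haemodynamic endpoint.

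**What to change.** 1. In the Table of Assessments and in the pre-procedure list of section 4, require the baseline walk on the day before or the same day as the procedure, and no more than 24 h before it. This brings it into line with the same-day baseline of the dyspnea questionnaire.
2. In section 12, state that the change in walk distance will be reported as supportive and descriptive, with its confidence interval and the actual time between walks, and not as evidence of block efficacy. This is needed because up to two days of usual-care drift remain for the 24 h walk, and up to three for the 48 h walk, without a control.

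The cost is a change of wording in two places and one sentence in the analysis section. A few late-consenting subjects may miss the baseline walk. Subjects who would have walked the day before anyway are unaffected.

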NCT02669407

1. Protocol Title:

Splanchnic Nerve Block for Therapy of Acute Heart Failure (Splanchnic HF)

2. Purpose of the Study:

Splanchnic vasoconstriction may contribute to decompensation of chronic heart failure via volume redistribution from the splanchnic vascular bed to the central compartment. This is a sympathetically mediated reflex and can be interrupted through a splanchnic nerve block. Therefore, we hypothesize that interruption of the efferent/afferent innervation of the splanchnic vasculature will decrease cardiac congestion and improve renal function in patients presenting with heart failure.

Objectives:

- 1. We will determine if splanchnic nerve blockade decreases cardiac preload as measured by invasive hemodynamics.
- 2. We will determine if splanchnic nerve blockade increases urine output.
- 3. We will determine whether splanchnic nerve blockade produces rapid improvement in creatinine clearance.

3. Background & Significance:

[figure not shown]
Conventional wisdom dictates that heart failure (HF) exacerbations follow a period of fluid accumulation leading to volume overload. However, study of weight in HF shows that 54% of patients have an exacerbation without antecedent weight gain. Invasive monitoring of hemodynamics showed that central venous pressure rises in the weeks prior to decompensation despite no weight change in both systolic and diastolic heart failure. The leading theory for explaining this phenomenon of increased central venous pressure in the absence of change in total body water is that patients with heart failure (HF) have impaired ability to store blood in their splanchnic vascular compartment. In a healthy population, the splanchnic bed contains about 40% of the total blood volume, 80% of which is stored in capacitance veins, and serves as a buffer for the central vascular compartment. Fluid is normally mobilized from this compartment via increased sympathetic tone and circulating catecholamines in response to a variety of physiologic and pathologic stressors. Given the role that the splanchnic circulation plays in hemodynamic regulation, it is hypothesized that increased sympathetic tone in the splanchnic vasculature contributes to both acute and chronic heart failure decompensation by mobilizing fluid to the central vasculature (Fallick C, Circulation Heart Failure 2011).

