Descriptive statistics of continuous outcomes will include sample size, mean, median, standard deviation, minimum and maximum. For categorical outcomes, the number and percentage of subjects in each category will be presented. Statistical comparisons will be made using t-tests for continuous outcomes and chi square or Fisher's exact test (depending on overall event rates) for categorical outcomes. Paired t-tests will be used to compare changes from baseline to post-intervention. All statistical analyses will be performed using SAS for Windows (version 8.2 or higher) or other widely accepted statistical or graphical software. Patient data listings and tabular and graphical presentations of results will be provided. Unless otherwise specified, a two-sided 0.05 level of significance will be used to declare change in pre- and post-procedure variables different.

For power analysis, our primary endpoint is decreased in central venous pressure following nerve blockade. Based on preliminary animal experiments, we anticipate a reduction of CVP of 25%. For a sample size of 16, If the true difference in the experimental and control means is 25%, we will be able to reject the null hypothesis that the population means of the experimental and control groups are equal with probability (power) .90. The Type I error probability associated with this test of this null hypothesis is 0.05.

There is no direct measure of technical success following attempted block of the splanchnic nerves. The location of the splanchnic nerves is estimated biased on human anatomy dissections and established nerve block protocols used by the anesthesiology department. Procedural success to block the splanchnic nerves will be assumed in 70% of the cases based on the experience in splanchnic nerve blocks in patients with intractable cancer.

13. Data & Safety Monitoring:

Due to the experimental nature of this intervention, data will be recorded after each subject completes the intervention for signs of unintended negative effects. These include hypotension, worsening renal function, or clinical deterioration. Additionally, patient's electronic medical data will be clinically screened for any traumatic complications from the nerve block for the first 24 hours postprocedure.

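### The Section 4 primary endpoint accepts a fall in any of three pressures, but the type I error of 0.05 and power of .90 in Section 12 belong to a single test of CVP, and no reading within 30-60 minutes is named.

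*Combined protocol and SAP*

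**What the plan says.** Section 4, under Efficacy endpoints, gives "Primary: Reduction in central venous pressure and/or pulmonary artery pressure (diastolic) and/or pulmonary capillary wedge pressure at 30-60 minutes after nerve block". It adds no rule for combining the three pressures.

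Section 12 states "For power analysis, our primary endpoint is decreased in central venous pressure following nerve blockade", with no time point. It then gives power .90 for a 25% reduction with a sample size of 16, and closes with "The Type I error probability associated with this test of this null hypothesis is 0.05". No other endpoint has a power statement.

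The general rules in Section 12 are "Paired t-tests will be used to compare changes from baseline to post-intervention" and "Unless otherwise specified, a two-sided 0.05 level of significance will be used to declare change in pre- and post-procedure variables different". No multiplicity adjustment is mentioned.

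Objective 1 in Section 2 names no single pressure: "We will determine if splanchnic nerve blockade decreases cardiac preload as measured by invasive hemodynamics". Under Procedure in Section 4, pressures are recorded roughly every 15 minutes for 1 to 1.5 hours after the block, so about three readings (30, 45 and 60 minutes) fall in the primary window. The plan does not say which of them, or what summary of them, is analysed.

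**The concern.** A reader of Section 4 would call the study positive if any one of the three pressures fell significantly. A reader of Section 12 would look only at CVP. The same data can satisfy the first and fail the second.

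The operating characteristics that the plan states belong to the CVP test alone. Three unadjusted tests with success on any one give a higher false-positive rate than the 0.05 quoted. The unnamed reading leaves a further choice open.

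The study is uncontrolled, so a primary test fixed in advance is its main protection against selecting the favourable pressure or time after the data are seen.

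**Working it through.** **Inputs from the documents.** n = 16, power .90, alpha 0.05, expected CVP reduction 25%, paired t-test, two-sided 0.05 (all Section 12); three pressures in the primary endpoint (Section 4); cap of 20 patients (Section 5).

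**Inputs not in the documents, so assumed.** The standard deviation (SD) of the change, and the correlation between changes in the three pressures (0.5 / 0.8 / 0.9, equal for all pairs). Changes are taken as normal. Figures for three pressures come from simulated paired t-tests, with at least 100,000 trials each, so the third decimal is uncertain.

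**Step 1: the plan's own figure.** Power .90 cannot be reproduced without an SD. Solving backwards with the noncentral t distribution (15 degrees of freedom, noncentrality d × √16), a paired two-sided 0.05 test has power .90 at d = 0.868. The implied SD is 25 / 0.868 = 28.8 percentage points. The power sentence is worded for two groups ("If the true difference in the experimental and control means is 25" percent); read that way, d would be 1.185 with 16 per group or 1.745 with 8 per group. I use 0.868 because the design is single-arm and the stated test is paired.

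**Step 2: false positives under the any-one rule, n = 16.** If the pressures were independent, at least one false significant change would occur with probability 1 − 0.95³ = 0.143, and at least one false fall with probability 1 − 0.975³ = 0.073. With correlation:

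| Correlation | Any significant change (one test: 0.05) | Any significant fall (one test: 0.025) |
|---|---|---|
| 0.5 | 0.13 | 0.063 |
| 0.8 | 0.10 | 0.050 |
| 0.9 | 0.085 | 0.043 |

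Results at n = 20 are practically the same.

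**Step 3: how often the two sections disagree, n = 16.**
- All three pressures respond with d = 0.868: any one falls significantly in 0.99 / 0.96 / 0.95 of trials, CVP alone in 0.90. The any-one rule is met without CVP in 0.09 / 0.06 / 0.05.
- That last figure depends on d: 0.24 / 0.15 / 0.11 at d = 0.6, 0.04 / 0.03 / 0.02 at d = 1.0, and under 0.01 at d = 1.185.
- Only wedge and diastolic pulmonary artery (PA) pressure respond (d = 0.868): the any-one rule is met in 0.97 / 0.95 / 0.93, CVP alone in about 0.025.

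**Step 4: Holm on three pressures.** The smallest p-value is compared with 0.05 / 3 = 0.0167, so this step determines the power for at least one fall. With d = 0.868:

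| Who responds | n = 16 | n = 20 |
|---|---|---|
| All three | 0.94 / 0.89 / 0.85 | 0.98 / 0.95 / 0.93 |
| CVP only | 0.77 | 0.88 |
| Wedge and diastolic PA only | 0.90 / 0.85 / 0.83 | 0.96 / 0.94 / 0.92 |

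**The case against.** **Section 12 may only be choosing a component for sizing.** Its sentence is qualified as being for the power analysis, CVP is one of the three pressures in Section 4, and nothing in Section 12 says that the other two are not primary. This is a fair reading, so the documents do not support the inference that the two sections flatly contradict each other. It does not remove the problem. If Section 4 governs, the any-one rule has no adjustment and no power basis, and its error is not the 0.05 stated.

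**The inflation is modest and depends on the yardstick.** This stands in part. Counting falls only, the rates of 0.063 / 0.050 / 0.043 lie near or below 0.05. They still exceed the 0.025 of a single test on the same footing, and counting changes in either direction the rates exceed 0.05 at all three assumed correlations.

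**The study is small and exploratory.** Section 4 says "the goal of the study is to demonstrate proof of concept". That limits the consequence, but the plan itself attaches a formal alpha and power to its primary test.

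**Stronger readings to avoid.**
- That all three pressures must fall, so that power drops below .90. The Section 4 wording ordinarily means that any one suffices, and nothing in the documents asks for all three, so this reading deserves little weight.
- That the leg raises at 30 and 60 minutes contaminate the primary readings. The plan schedules them to observe breathlessness and never says that pressures are recorded during them.
- That the plan permits picking the best reading. It is silent on the reading, which is a gap and not a licence.

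**Conclusion.** The point holds and should be fixed. The mismatch between a three-pressure primary endpoint and error and power figures for CVP alone is on the page and needs no assumption. So is the missing choice of reading or summary within the window.

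The size does rest on assumptions. The chance of at least one false significant change is about 0.13 to 0.085 for correlations of 0.5 to 0.9, against the stated 0.05. How often a trial would meet Section 4 and miss CVP ranges from under 0.01 to 0.24 when all three pressures respond equally (d from 1.185 down to 0.6). It is far higher if CVP is the one that does not respond. The documents give neither the effect size nor the correlations, so these figures show that the divergence is possible and do not predict its frequency. Whether n = 16 really gives power .90 for CVP is a separate question, not decided here.

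**What to change.** **Preferred, consistent with Section 12.** In Section 4, replace the primary endpoint with text such as: *Primary: change in catheter-measured CVP from the pre-block baseline to the mean of the scheduled readings 30 to 60 minutes after the block; paired t-test, two-sided 0.05; met if the fall is significant. Secondary: wedge pressure and diastolic PA pressure, same summary, tested in a prespecified order, each only if the preceding test shows a significant fall.*

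The mean is an example; any single summary fixed in advance will do. The order of the two secondaries is for the sponsor to choose, since the documents give no basis for one. Catheter-measured is needed because Section 4 also lists an echocardiographic CVP among the secondary endpoints.

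Cost: wording only, with no added patients or measurements. The downside is that a fall confined to wedge or diastolic PA pressure would not be a positive primary result, which is narrower than Objective 1.

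**Alternative, if the sponsor keeps all three under Objective 1.** State that one significant fall suffices, fix the same summary, apply Holm at an overall two-sided 0.05, and rewrite the endpoint and power sentences in Section 12 to match. This is also a change of text, but the stated .90 is not always kept, as the Holm table shows: at d = 0.868 with CVP alone responding, power is 0.77 at n = 16 and 0.88 at the cap of 20.
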